3.5 Data Analysis

Sample size estimation for this interobserver agreement study was based on a confidence interval approach⁹. Using 4 raters and 3 levels of rating for their assessment, with type I error (alpha) fixed at 0.05 and an expected 80/20 probability of the absence or presence of craniosynostosis, respectively, we will have 80% power to claim the interobserver kappa statistics is greater than 0.7 when the true kappa is 0.95 with a sample size of 37

patients. Interobserver agreement will be summarized by the kappa coefficient statistic and corresponding 95% confidence intervals.

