Comparative Analysis of Zero Echo-time MRI and CT for Pediatric Craniosynostosis

NCT#04704284

23May2022

Title of the Study: Comparative analysis of zero echo-time MRI and CT for pediatric craniosynostosis. Ver 3 May 23, 2022.

Principle Investigator: [name] Neuroradiology

Abstract

Zero echo-time (ZTE) MRI (K132376) is an emerging technique that has been shown to adequately image bone and will likely allow eventual widespread imaging of osseous structures. The opportunity to exchange standard CT evaluation for a radiation-free modality is desirable, particularly in the pediatric population. A promising clinical application is the use of ZTE for diagnosing craniosynostosis, potentially precluding the use of the standard volumetric head CT scan. We propose a comparative analysis between zero echo-time MRI and CT to assess their effectiveness in diagnosing this entity. Our hypothesis is that ZTE is concordant with CT for suture visualization and imaging diagnosis, permitting its use in the clinical setting for this purpose.

Research Plan

1. Specific Aims

To establish whether ZTE imaging of the infant calvarium can provide equivalent information to CT and allow for a reliable diagnosis of craniosynostosis in a child. This aim is based on the hypothesis that there will be 90% or greater concordance between ZTE and CT findings.

2. Background & Significance

Magnetic resonance imaging (MRI) has become the primary workhorse for pediatric neuroradiology, providing superior imaging of soft tissues in the brain, head, neck and spine, while offering the added benefit of having no ionizing radiation. Evaluating cortical bone, however, continues to be a limitation with conventional MRI sequences. The contents within cortical bone (inorganic minerals, collagen matrix and various water concentrations) and their tightly organized structure result in very short T2 values ($T2 \sim 300-400 \,\mu s$) and rapid magnetization decay which yield signal voids and insufficient image contrast.

Computed tomography (CT), therefore, continues to be the primary modality for evaluating osseous structures. This modality is not ideal in children who have increased sensitivity to the adverse effects of radiation. Developing a comparable MR sequence which can evaluate bone without radiation is critical and aligns with the ALARA ("as low as reasonably achievable") radiation safety principle to minimize radiation doses in children.

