Three dimensional proton density-weighted zero echo-time (ZTE) is a developing technique that uses proton density differences rather than T2 relaxation time differences to achieve contrast. It has been used to better image bone structure within the calvarium, spine and

extremities¹⁻⁵ and has been explored for use in attenuation correction for PET/MR studies⁶⁻⁸. The sequence is performed without preparation pulses or multiple echoes, rendering it time-efficient and (if performed alone), usually precluding the need for sedation¹. Alternatively, it can easily be added to a more complete MR exam, providing an efficient "one stop" evaluation.

The diagnostic utility of ZTE is not yet established and a comparative validation study of ZTE with CT is needed before reliably using this in the clinical setting for preoperative purposes. If ZTE is shown to be non-inferior to CT for evaluation of craniosynostosis, clinical practice will be substantially improved; neurosurgeons as well as parents and children may be offered a radiation free imaging tool. This is particularly advantageous for this population of children which may require multiple follow-up exams after surgical correction. Moreover, this could serve as an initial study preceding evaluation of other osseous structures including facial bones and skull base. The findings in this study could also drive further technological advancements to include the creation of surface renderings based on ZTE data for anatomic modeling.

3. Study Design

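### The only planned statistic, interobserver kappa, never compares ZTE with CT, so the plan as written cannot test the hypothesis of 90% or greater ZTE-CT concordance

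*Combined protocol and SAP*

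**What the plan says.** The question is stated three times, always between modalities.

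- Abstract: "Our hypothesis is that ZTE is concordant with CT for suture visualization and imaging diagnosis".
- Section 1, Specific Aims: "This aim is based on the hypothesis that there will be 90% or greater concordance between ZTE and CT findings".
- Section 2, Background & Significance, in a conditional sentence about clinical benefit: "If ZTE is shown to be non-inferior to CT for evaluation of craniosynostosis". No margin is given anywhere.

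Sections 3.3 and 3.4 have the same four neuroradiologists rate CT and ZTE in separate blinded sessions at least two weeks apart. They score suture and fontanelle visibility from 1 to 3, and the diagnosis as present, absent or unable to tell.

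Section 3.5 is the whole analysis plan. It opens with "Sample size estimation for this interobserver agreement study was based on a confidence interval approach", sizes the study at 37 patients to show interobserver kappa above 0.7 when the true value is 0.95, and ends with "Interobserver agreement will be summarized by the kappa coefficient statistic and corresponding 95% confidence intervals". It does not say whether kappa is computed on CT, on ZTE or on both. No section defines a ZTE-CT concordance estimate, an intermodality kappa, sensitivity or specificity against CT, or a rule for judging the 90% threshold.

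**The concern.** Reader agreement and modality agreement are different quantities. Four readers can agree perfectly on ZTE and all be wrong in the same patients if the sequence fails to display the abnormality. Visibility has the same problem: if every reader scores a suture 3 on CT and 2 on ZTE, agreement within each modality is complete while ZTE is plainly worse.

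The abstract ties the result to clinical use of ZTE in place of CT. A report that follows section 3.5 to the letter could show high kappa and be taken as validation without estimating how often ZTE and CT give the same answer, or how many CT-positive children ZTE misses. If the comparison is instead designed after the ratings are seen, the choices left open (unit, reference read, handling of unable-to-tell, estimate or lower limit) could decide the verdict.

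**Working it through.** **1. What the sample size is about.** Inputs from section 3.5: 4 raters, alpha 0.05, 80/20 absent/present, 80% power, kappa 0.7 against 0.95. A goodness-of-fit calculation for 4 raters under a beta-binomial model with two categories uses

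N = (z_alpha + z_power)² / Σ[(P1 − P0)² / P0],

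where P0 and P1 are the probabilities of 0 to 4 positive calls at kappa 0.7 and 0.95. The sum is 0.1695. With one-sided alpha, N = (1.645 + 0.842)² / 0.1695 = 36.5, so 37. This shows that the stated figure is attainable, not that this was the method used: two-sided alpha gives 47, and the text states three rating levels and no sidedness. No ZTE-CT concordance parameter enters the calculation.

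**2. A counterexample needing no assumption about reader error.** The stated 20% prevalence gives 0.2 × 37 = 7.4, so take 7 CT-positive patients. All four readers call those 7 positive on CT. On ZTE all four call the same 3 of the 7 positive and everyone else negative.

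- Interobserver kappa: 1.0 on CT and 1.0 on ZTE, since no two readers ever differ.
- ZTE-CT concordance: (3 + 30)/37 = 33/37 = 89.2%, below 90%.
- ZTE finds 3 of 7 CT-positive patients (42.9%).
- Intermodality kappa: chance agreement is (7×3 + 30×34)/37² = 1041/1369 = 0.760, so kappa = (0.892 − 0.760)/(1 − 0.760) = 0.55.

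A perfect result on the planned analysis is compatible with failing the stated hypothesis.

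**3. With imperfect readers.** Assume each reader is right with probability *a* about what the images show. In large samples, interobserver kappa ≈ 1 − a(1 − a)/[P(1 − P)], with P = πa + (1 − π)(1 − a), where π is the share of patients in whom that modality displays the abnormality. The formula contains nothing about whether ZTE and CT display the same patients.

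- CT, π = 0.2, a = 0.995: P = 0.203, kappa ≈ 1 − 0.004975/0.1618 = 0.97.
- ZTE hiding half the cases, π = 0.1, a = 0.995: P = 0.104, kappa ≈ 1 − 0.004975/0.0932 = 0.95.

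Simulated means for trials of 37 patients (20% prevalence, a = 0.995), with CT kappa 0.97 throughout:

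| True cases displayed on ZTE | Mean ZTE kappa |
|---|---|
| 100% | 0.97 |
| 80% | 0.96 |
| 70% | 0.95 |
| 60% | 0.94 |
| 50% | 0.93 |

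With half the cases hidden, the ZTE kappa estimate exceeds 0.7 in about 96% of trials, while mean concordance is about 89% and falls below 90% in about 55% of them.

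**4. Sensitivity to reader accuracy** (an assumption, not in the documents). With half the cases hidden, mean ZTE kappa is 0.93, 0.87, 0.77 and 0.57 at accuracies of 99.5%, 99%, 98% and 95%. At 95%, CT kappa itself is only about 0.72. The plan's own true kappa of 0.95 corresponds to accuracy between 99% (P = 0.206, kappa ≈ 1 − 0.0099/0.1636 = 0.94) and 99.5% (0.97).

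**5. What 37 patients give for the actual hypothesis.** Take one paired result per patient and exact binomial limits.

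| Agreement | Estimate | Exact 95% lower limit |
|---|---|---|
| 34/37 | 91.9% | 78.1% |
| 36/37 | 97.3% | 85.8% |
| 37/37 | 100% | 90.5% |

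Only 37/37 clears 90% on the lower limit. The chance of that is p³⁷: 15%, 32% and 69% if true concordance is 95%, 97% and 99% (assumed values).

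**The case against.** The strongest reply is that the design does not prevent the comparison. The same readers rate both modalities on the same scales, the title and aim announce a comparison, and section 3.7 anticipates 40 further hours of statistical work. On that view this is a thin plan, not a wrong one. It is true that the paired data will exist, and the fault lies in the analysis plan, not the data. But an announced aim is not an analysis, and section 3.5 names a specific statistic that answers another question.

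Three narrower points stand:

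- The 0.7 is the null value in a power statement. No section says that kappa above 0.7 validates ZTE, so the risk is one of interpretation.
- The simulated kappas depend on near-perfect readers and omit the unable-to-tell level, which readers might use when ZTE shows a suture poorly. The counterexample depends on neither.
- Overall concordance is itself forgiving at 20% prevalence. Hiding 30% of cases costs about 0.2 × 30% = 6 points, leaving roughly 93–94%, which would usually meet 90% on the estimate. Replacing kappa with overall concordance alone would therefore not be enough.

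The non-inferiority wording is background, not a stated objective. The finding does not need it.

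**Conclusion.** The concern holds and must be fixed before analysis. The study's one hypothesis has no defined estimate, no analysis, no decision rule and no sample-size basis, and the statistic that is planned can be perfect (1.0 on both modalities) while concordance is 89.2% and ZTE finds 3 of 7 cases. That conclusion follows from the documents and simple arithmetic. The simulated ZTE kappas of 0.93 to 0.97 additionally assume 99.5% reader accuracy, which is broadly in line with the plan's own planning value for kappa.

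**What to change.** Rewrite section 3.5 so that the paired comparison comes first.

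- **Primary analysis:** concordance of the diagnosis rating between ZTE and CT, comparing each reader's ZTE call with the same reader's CT call, and with the majority CT call. State how a 2–2 split on CT is resolved.
- **By CT status:** report agreement separately in CT-positive and CT-negative patients, and say what would be acceptable in the CT-positive group. Expect little precision there: 7/7 has an exact lower limit of 59%.
- **Unable to tell:** fix its handling in advance. Counting it as not concordant in the primary analysis, with a sensitivity analysis excluding it, would be conservative.
- **Intervals:** 95% limits treating the patient as the cluster, for example a patient-level bootstrap or GEE.
- **The 90% threshold:** state whether it applies to the estimate or to the lower limit.
- **Visibility:** paired ZTE-minus-CT difference for each suture.
- **Secondary:** interobserver kappa, separately for CT and ZTE.

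The direct cost is plan wording and a few hours of analysis, since every rating needed is already collected. The statistical cost is wider intervals than pooling 4 × 37 = 148 reads would suggest: effective n = 148/(1 + 3ρ), which is about 93, 59 and 44 for assumed within-patient correlations of 0.2, 0.5 and 0.8.

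If the lower limit must exceed 90%, 37 patients are too few unless agreement is complete. With one paired result per patient, 80% power at one-sided 0.025 needs 231, 100, 70 or 54 patients for true concordance of 95%, 97%, 98% or 99%. If the sponsor keeps 37, the plan should say that concordance will be estimated with its interval, and that a lower limit above 90% is not expected short of near-complete agreement.

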3.6 Associated staff

A research coordinator ([name]) will work with the ordering staff from the plastic surgery or neurosurgery group and the radiology schedulers to arrange for scheduling the CT and MRI exams for the patient. The research coordinator will also be contacting or meeting patient before the scans to obtain consent. Biomedical Imaging Resource (BIR) will create a viewing platform that will be used to evaluate the de-identified images presented in a randomized and blinded fashion. Statistics support will be used for data analysis.

3.7 Budget and Research Category B Time

Funding will go to research coordinators, statistics, and BIR for their contributions as detailed above. Statistics has used approximately 4 hours for study planning and anticipates an additional 40 hours for performing statistical analysis, preparation of publication tables and figures, as well as abstract and manuscript support. Research category B days are requested for the neuroradiologists who will be involved with project management/organization for MRI and the time intensive process of evaluating both ZTE and CT images for the multiple criteria detailed above. Time will also be used for data interpretation, manuscript drafting, editing and submission.

